With respect to HIV, INF has shown antiviral activity both in vitro (Ho, Hartshorn et al. 1985) and in vivo (Lane, Kovacs et al. 1988, Hatzakis, Gargalianos et al. 2001). The major activity of INF against HIV is thought to be the inhibition of the release of progeny virions from host-infected cells (Poli, Orenstein et al. 1989, Gottlinger, Dorfman et al. 1991). This anti- HIV-1 activity is opposed by the viral protein Vpu (Gottlinger, Dorfman et al. 1993) and recently the cell protein that mediates viral retention was identified as an INF-induced protein, Bst-317 or tetherin (Neil, Zang et al. 2008). In addition it is known that retroviral restriction factors such as APOBEC3G and TRIM5 α are INF-regulated genes and their induction might also play a role in INF antiviral activity (Goff 2004). A number of in vitro studies suggested that the effects of interferon were modest (2-8 fold reductions in viral RNA) but interestingly, the combination of interferon and early antiretrovirals, such as AZT, was markedly synergistic (Hartshorn, Vogt et al. 1987), including in vitro models of cells chronically infected with HIV-1. These results are particularly intriguing because in cultures of chronically infected cells, the majority of the cells produce HIV-1 from integrated proviruses, and there is little spreading infection; as a result, AZT has minimal or no direct antiviral effect, and interferon may have been the most potent antiviral in these experiments (Poli, Orenstein et al. 1989). Experiments with HIV-1 production from chronically infected cells may represent a

useful model for participants suppressed on antiretroviral therapy as experiments suggest the majority of the detectable virus is produced from cells with integrated proviruses. Although interferon has been studied in active spreading infections, little data are available from participants who are already suppressed on ARV.

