In the pre-ART era, INF clinical trials showed a degree of efficacy in reducing viral replication, p24 production, and slowing progression to AIDS (de Wit, Schattenkerk et al. 1988, Lane, Davey et al. 1990, Berglund, Engman et al. 1991). After development of combination ARV, however, INF was not developed as an antiretroviral, due to lower antiviral efficacy, inconvenient route of administration, and adverse effects (Lane, Davey et al. 1990, Dusheiko 1997). Recently, several groups have shown a substantial HIV RNA reduction in participants treated with the pegylated form of interferon alpha (PEG-INF) as part of chronic hepatitis C therapy (Torriani, Ribeiro et al. 2003, Talal, Shata et al. 2004, Neumann, Polis et al. 2007). In addition, Asmuth and colleagues recently studied the effect of pegylated interferon alpha on HIV viral load in HBV/HCV seronegative HIV-1-infected participants who were not receiving antiretroviral therapy. HIV-1 viremia declined by a mean 0.77 log₁₀ copies/mL over 12 weeks (Asmuth D 2009).

The mechanism of interferon effect on HIV viremia is uncertain. There is a substantial literature regarding the effects of interferon in retroviruses in vitro, and in HIV in particular (Pitha 2011). Interferon may induce expression of a number of innate immune responses, which have direct effects on a number of distinct steps in virus replication. Induction of the cellular gene APOBEC 3G and 3F can result in hypermutation of the HIV genome during reverse transcription (Goila-Gaur and Strebel 2008). Induction of the gene tetherin results in retention of HIV on the surface of infected cells and decreases in production of extracellular HIV virions (Perez-Caballero, Zang et al. 2009). The effects of interferon may be manifest as a decrease in peripheral viremia, and a corresponding accumulation of HIV RNA intracellularly.

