2.1 Primary Objective

This is a non-randomized, single arm pilot study of 10 participants to investigate the effect of interferon alpha on HIV-1 production in plasma and peripheral blood lymphocytes from HIV-infected individuals with HIV-1 RNA levels below the limit of detection in commercial assays.

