3.2.2.1 Primary End Points

We will compare viral RNA levels in blood and peripheral blood lymphocytes drawn before, during, and after intensification, including comparison of absolute values of viremia, as well as changes in viremia and area under the curve analyses to detect whether increases or decreases of viremia occurred as a function of interferon therapy. Standard analyses will be included.

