9.5 CD4 Counts

CD4 counts (absolute number and percentage) will be measured at Pre-entry, Entry, Visits 1, 4, 8, 9 and the Final Study or Discontinuation Visit. Samples will be processed according to standard flow cytometry procedures.

10 Statistical Considerations

This pilot study will investigate whether pegylated interferon alpha2-b will reduce residual HIV-1 RNA in participants with HIV-1 viremia suppressed below detectable levels as measured by commercial assays. Two relevant questions are: 1) does intensification reduce viremia in a consistent way across different patients, and 2) are there *any* patients in whom intensification reduces viremia? The first question is of primary interest, and it pertains to the population. The second question concerns whether individual intensification responders can be identified. It is possible to find no consistent pattern across patients, yet identify one or more patients in whom the pattern of viremia lowering over time convincingly rules out a flat slope for that patient. Therefore, analyses will be directed at both population responses and individual responses, with the primary emphasis being on the former.

For both population and individual analyses, one complication is that because patients are selected on the basis of low baseline viral loads, regression to the mean would cause subsequent viral loads to be somewhat larger, in the absence of intensification. To account for this, we will use one baseline measurement to determine eligibility and another to assess changes over time.

The primary analysis (which is at the population level), compares the viral loads obtained from the pre-intensification control period to the week 4 value using a paired t-test. A sensitivity analysis will use the nonparametric Wilcoxon signed rank test to analyze these baseline to week 4 changes. Another analysis computes the slope of viral load over time for each patient, and uses a 1-sample t-statistic and confidence interval to estimate and test whether the average slope is 0.

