Secondary analyses will attempt to identify individual intensification responders. One definition of responder is whether the patient had at least a 1-log decrease from baseline to 4 weeks in viral load. Because patients with baseline viral load below 10 cannot achieve this, another method will compute the least squares slope of viral load versus time for each patient and declare patients with statistically significant slopes as responders. Because the goal for this analysis is to summarize the response of a given individual, we treat the data as independent observations from that patient. This is the same assumption made when using a mixed model, namely that conditioned on the random, patient-specific intercept and slope, the observations are independent. For both the 1 log method and significant slope method of identifying individual responders, we attempt to find differences in baseline characteristics between responders and non-responders, though very low power precludes finding any of these statistically significant unless they are huge. Of particular interest is whether baseline viral load predicts responder status. As described above, for this analysis we will use one baseline value to characterize baseline viral load and another for the calculation of slope to identify responder status.

All tests will be two-sided and an alpha level of less than 0.05 will be considered statistically significant. Analyses will be performed on both intent-to-treat and as per protocol participants. Any dropouts and non-adherent participants will be replaced. We do not feel that stopping criteria are necessary as this pilot study is not for prognosis or clinical management; there is no blinding of study treatment and we will be monitoring toxicities in real time. In this study, we will be studying participants on an ongoing basis, and no interim analysis is planned.

11 Sample Size Estimation

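### Section 10 does not fix the scale, baseline visit or below-limit rule for the primary viral-load test: specify log10, average the two pre-dose SCA values, and plan the cell-associated RNA comparison

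*Combined protocol and SAP*

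**What the plan says.** Section 10 describes the primary, population-level analysis as one that "compares the viral loads obtained from the pre-intensification control period to the week 4 value using a paired t-test". A Wilcoxon signed rank test on the same changes is the sensitivity analysis, and a one-sample t-test on patients' slopes is a further analysis. None of the three has a stated scale. The word log appears in Section 10 only in the secondary responder definition, "at least a 1-log decrease from baseline to 4 weeks in viral load", followed by the remark that "patients with baseline viral load below 10 cannot achieve this".

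On baseline, Section 10 says "we will use one baseline measurement to determine eligibility and another to assess changes over time". It names no visit. Sections 5.2 and 5.4, Section 9.2 and Appendix 1 schedule the single copy assay (SCA) at screening, Pre-entry 1 and Day 0.

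The primary objective concerns "HIV-1 production in plasma and peripheral blood lymphocytes", and Section 3.2.2.1 compares RNA in both compartments, "including comparison of absolute values of viremia", together with changes and areas under the curve. Section 10 has no analysis of cell-associated RNA. The Précis expects some plasma values below the limit of detection, Section 13 gives the SCA limit as 0.1 copies/mL, and no rule for such values appears anywhere.

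The Introduction expresses effects in relative terms: in vitro, "the effects of interferon were modest (2-8 fold reductions in viral RNA"; and in patients not on antiretroviral therapy, "HIV-1 viremia declined by a mean 0.77" log10 copies/mL.

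**The concern.** The t-test cannot be run until the scale, the baseline and the treatment of low values are chosen, and the plan leaves each choice open in an unblinded single-arm study. They are not cosmetic. If interferon lowers RNA by a similar factor in each patient, copies/mL differences are dominated by the few patients with high levels, while log10 differences weight patients alike. Using one of two available pre-dose SCA results discards information already collected. The text also implies two floors: the remark about baselines below 10 is true only with a floor of 1 copy/mL, whereas Section 13 gives 0.1. Finally, half of the primary end point has no planned test, so neither its analysis nor its standing relative to plasma is settled.

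**Working it through.** **The plan's own figure.** The only sizing figure is in Section 11: the upper limit for 0 of 10 suppressed. The two-sided 90% Clopper-Pearson limit is 1 − 0.05^(1/10) = 0.259, which matches the table's 0.26. The text's 21% is the one-sided limit, 1 − 0.10^(1/10) = 0.206. Neither concerns the paired t-test, for which the plan gives no SD, effect size or power.

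**Baseline averaging.** Let s be the within-patient SD on log10.
- One baseline: SD of the change = s√(1 + 1) = 1.414s.
- Mean of two baselines: s√(1/2 + 1) = 1.225s.
- Ratio: 1.225/1.414 = 0.866, a 13% cut.
- With n = 10 and two-sided 0.05, 80% power needs a mean change of 0.996 SDs of the change. At an assumed s of 0.2, 0.3, 0.4 and 0.5, the detectable log10 change goes from 0.28 to 0.24, 0.42 to 0.37, 0.56 to 0.49, and 0.70 to 0.61. This ignores values below the limit.

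**Scale.** Simulation of n = 10 with 20,000 trials per case. Assumptions: true fall 0.5 log10 (3.2-fold), median 1 copy/mL, one baseline, values below 0.1 set to 0.1. Noise is either lognormal (SD 0.3) or count-like (Poisson on an assumed 10 mL, plus SD 0.1). Power of the paired t-test:

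| Between-patient SD (log10) | Lognormal: log10 / copies | Count-like: log10 / copies |
|---|---|---|
| 0.1 | 0.91 / 0.77 | 0.99 / 1.00 |
| 0.3 | 0.91 / 0.61 | 0.99 / 0.94 |
| 0.5 | 0.89 / 0.39 | 0.98 / 0.71 |
| 0.7 | 0.85 / 0.25 | 0.96 / 0.46 |
| 0.9 | 0.81 / 0.17 | 0.94 / 0.35 |

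At SD 0.7 with lognormal noise, log10 with two baselines gives 0.94. An exact Wilcoxon test on copies/mL with one baseline gives 0.73, so it recovers part of the loss. With no true effect, the log10 test with two baselines and substitution at 0.1 rejects 4.0–5.0% of the time, and the copies/mL test with one baseline 1.1–2.7%. The gain is therefore not bought with extra false positives.

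**Floor.** Two baselines, log10, between-patient SD 0.7, lognormal noise, true fall 0.50:
- Median 1: a floor of 1 gives an estimated fall of 0.18 and power 0.47; a floor of 0.1 gives 0.42 and 0.94. Day 28 values at the floor: 76% versus 26%.
- Median 3: a floor of 1 gives 0.30 and 0.81; a floor of 0.1 gives 0.47 and 0.96.

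**Why substitution should not supply the estimate.** Section 13 reports 10 of 36 people eligible at ≥0.38 copies/mL in the earlier raltegravir study. If the other 26 all failed on RNA and the between-patient SD is 0.7, the median is 10^(log10 0.38 − 0.589 × 0.7) = 10^(−0.833) = 0.147. Substituting 0.1, with two baselines:
- Median 0.147, unscreened: estimated fall 0.23, 95% CI covers the true 0.50 about 30% of the time. A 3.2-fold fall is reported as 10^0.23 = 1.7-fold.
- Median 0.147, screened at ≥0.1: 0.35, coverage about 72%.
- Median 1: 0.42, coverage about 88–89%.

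**The remark about 10.** A 1-log fall from baseline B ends at B/10, which must be at or above the limit L to be shown, so B ≥ 10L. With L = 1, B ≥ 10. With L = 0.1, B ≥ 1.

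**Cell-associated RNA.** Section 9.4 stores PBMC at Entry, Visit 4 and the final visit. Sections 5.4 and 5.6 list them for storage. After screening, the visit lists name cell-associated assays only at Weeks 16, 24, 36 and 48. Two co-equal tests at 0.05 would carry an error of 1 − 0.95² = 9.75% if independent.

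**The case against.** A reader might infer that the plan commits the primary test to copies/mL. It does not. In Section 3.2.2.1 absolute values are set against changes, so the phrase may mean levels rather than untransformed units, and the cut-off of 10 belongs to the responder rule. A virologist might well take logs anyway. The scale is unstated, and the copies/mL column sizes one possible reading.

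A reader might also infer that the trial misses a power target, or that baseline is left wholly uncontrolled. Neither is supported. Section 11 sizes on precision for a proportion and calls the study a pilot. Section 10 does separate the eligibility value from the change baseline, and its plural for the control period against a single week 4 value could suggest pooling. Yet the sentence on regression to the mean describes one other measurement, so averaging two is a choice that must be written down.

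The remaining objections have weight. Every SD, median and noise model here is assumed, and under count-like noise the scale hardly matters at between-patient SD 0.1–0.3. The Wilcoxon test protects in part, but it is only the sensitivity analysis and needs the same baseline and low-value rules. Substitution at 0.1 is one convention among several: at median 0.147 unscreened, 0.05 gives an estimated fall of 0.31 against 0.23. That argues for a rule fixed in advance and for not resting the estimate on substitution.

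**Conclusion.** The point holds as a specification gap with two concrete improvements: log10 and the mean of two pre-dose baselines. The baseline gain, 13% off the SD of the change, needs only equal and independent within-patient errors and few values below the limit. The scale gain depends on how widely patients differ: in the table it runs from nil (count-like noise, SD 0.1) to 0.85 against 0.25 (lognormal, SD 0.7) and beyond. It presumes a roughly common fold fall; if the log fall itself varies with SD 0.3, the lognormal figures are 0.76/0.43, 0.73/0.28 and 0.68/0.18 at between-patient SD 0.3, 0.5 and 0.7.

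The floor matters most when levels are low. Moving it from 0.1 to 1 more than halves the estimated fall at median 1, but not at median 3. The error in the remark about baselines below 10 and the missing cell-associated analysis depend on no assumption. This should be changed, but it does not invalidate the design.

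**What to change.** In Section 10:

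1. Define the primary plasma test as a paired t-test on the change in log10 SCA RNA from the mean of the Pre-entry 1 and Day 0 (pre-dose) log10 values to Day 28, excluding the screening eligibility sample. Put the Wilcoxon test and the population slope on log10 too.
2. State one below-limit rule in advance. Substitution at a named value may serve the hypothesis test. Take the fold change and its 95% CI from a left-censored random-intercept model, and report the number of values below the limit at each visit. With ten patients that interval is itself approximate; its coverage was not simulated here.
3. Restate the responder remark: at a limit of 0.1 copies/mL, the baseline below which a 1-log fall cannot be shown is 1, not 10.
4. Add a comparison of log10 cell-associated RNA per million PBMC from Day 0 to Day 28, with that assay's limit and low-value rule, and state that the stored cells from those visits will be assayed. Exclude the screening value: entry requires at least 5 copies per million there, so regression to the mean would imitate a fall. Day 0 alone is the safer cell baseline, because Section 9.4 and Appendix 1 disagree on PBMC at Pre-entry 1.
5. State that plasma is tested first and cell-associated RNA second, or give another multiplicity rule.

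Align Section 3.2.2.1 with these definitions. The cost is wording, a little more analysis, and assays on samples already stored; no visits or blood draws are added. The downside is that results are fold changes rather than copies/mL differences.

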plasma HIV levels were detected (using an assay with a 4-5 copy limit of detection ,approximately 30 fold higher than the single copy assay. Differences in levels of cell associated DNA were detected, but no studies of intracellular HIV RNA were performed(Azzoni, Foulkes et al. 2013).Recently intracellular HIV RNA may be recognized by intracellular toll like receptors,which are themselves induced by interferon. As such the effects of interferon on cell associated HIV RNA are of growing interest. Recently we have developed digital droplet methods to quantify HIV RNA levels in infected cells, including levels of unspliced, spliced, and short (tat⁻) transcripts, which may be synthesized in latently infected cells not producing full length HIV RNA. In combination with single genome sequencing, these approaches will be useful in investigating the effects of interferon alpha in HIV infected individuals, including determining overall levels of cell associated RNA, numbers of cells producing HIV RNA, and phylogenetic analysis of HIV RNA sequences in plasma and cells. This advance will permit us to investigate the effects of interferon in patients with and without detectable levels of HIV RNA in plasma; patients with levels of HIV RNA below levels of single copy detection are still be detectable by measurements of HIV RNA .

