This is a pilot study of the effect of pegylated interferon on HIV-1 RNA levels in participants who are receiving antiretroviral therapy. To date, there is limited published data available, and the proportion of participants who will respond with decreases in HIV-1 viral RNA levels remains to be clearly defined. As described above, responses may be similar to those observed with PI, integrase inhibitor, or NNRTI intensification, where no participants have experienced a decrease in viral RNA levels. If so, previous sample size analyses estimating the frequency of suppressible participants are relevant. In the accompanying table, we estimate the 90% confidence intervals of the probability that a participant has a detectable decrease in viral RNA levels (participants suppressed in the table below) after studying increasing numbers of participants without observing episodes of drug suppression. As shown here, if we study 10 participants and observe no

suppression in plasma or cell-associated HIV RNA, we have 90% confidence that the frequency of suppressible participants is less than 21%. For this pilot study, we will request a sample size of 65 participants to achieve our goal of studying 10 participants who have ≥ 0.1 copies/mL HIV-1 RNA at screening.

90% exact confidence intervals (using the Clopper-Pearson method) for the probability of being suppressible.

Participants intensified	Participants suppressed	90% confidence interval
5	0	0,0.45
6	0	0,0.39
7	0	0.0.35
8	0	0,0.31
9	0	0,0.28
10	0	0,0.26
15	0	0,0.18
20	0	0,0.14

12 Hazards/Discomforts/Risks

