12.2 Human Subject Protections

Participants will be fully counseled prior to entry into the study as to the potential risks of the study. Participants who, in the opinion of the study team, do not fully comprehend these potential risks will not routinely be offered participation in the study. Participants will be monitored closely during their participation in the study, and informed of any new information regarding the study treatment that may influence their willingness to continue study participation.

13 Study Recruitment

The study will be advertised and posted on the NIH web site. The University of Pittsburgh AIDS Clinical Trials Unit will recruit participants from its Volunteer Registry. IRB-approved recruitment materials will be distributed among AIDS service organizations and other HIV providers in the region. Both the NIH and the University of Pittsburgh have recently completed drug intensification studies and have been successful in enrolling participants willing to complete the frequent visits.

In the most recent study, we used the current viral RNA enrollment criterion (≥ 0.38 copies/mL) to study raltegravir intensification; 36 participants were screened for the study and 10 were eligible; the remainder were excluded chiefly on the basis of viral RNA levels. Nevertheless, 9 of the 10 enrolled participants completed this study and had evaluable data that were useful in determining whether viremia decreased. To improve our statistical analysis, we have increased the sensitivity of the assay (lower limit of quantification = 0.1 copies/ml) and will use 0.1 copies/ml as cutoff.

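### The 1-log responder rule cannot be met from a baseline below ten times the assay limit, yet it is applied to all patients when asking whether baseline viral load predicts response

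*Combined protocol and SAP*

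**What the plan says.** Section 10 gives two definitions of an individual responder. The first is: "One definition of responder is whether the patient had at least a 1-log decrease from baseline to 4 weeks in viral load". The second, a statistically significant least-squares slope, is introduced because of a floor: "Because patients with baseline viral load below 10 cannot achieve this, another method will compute the least squares slope". No unit is given; copies/mL is assumed here.

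Section 10 then compares baseline characteristics of responders and non-responders under both definitions, and adds: "Of particular interest is whether baseline viral load predicts responder status". One baseline value is to serve as the predictor and a different one is to enter the slope. Section 10 has no category for patients who cannot reach 1 log and no rule for results below the assay limit.

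The documents do not agree on that limit. Section 1 describes ultrasensitive assays as reaching 1 copy/mL, and Section 3.1 names the trial's assay as one that resolves a single copy per mL. Section 13 says "we have increased the sensitivity of the assay (lower limit of quantification = 0.1 copies/ml) and will use 0.1 copies/ml as cutoff", and Section 11 repeats the figure as "our goal of studying 10 participants who have ≥ 0.1 copies/mL HIV-1 RNA at screening". Section 1 also describes another study's assay, with a limit of 4 to 5 copies, as "approximately 30 fold higher than the single copy assay".

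**The concern.** A 10-fold fall can be recorded only if the baseline is at least ten times the lowest value the assay can report. Section 10 recognises this and adds a second definition, but it keeps the first one in the comparison where the floor does most damage. Baseline viral load decides who is able to meet the 1-log rule, and baseline viral load is also the predictor under test. Patients with low baselines are counted as non-responders whatever interferon does to them. The comparison would then tend to show response concentrated in patients with higher baselines even if the drug acted equally at every baseline.

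The stated floor of 10 matters as a symptom. It shows that Section 10 rests on a different assay limit from Section 13, so a reader cannot tell which patients the floor affects.

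**Working it through.** **Inputs**

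- Response: a fall of at least 1 log10 (10-fold), baseline to week 4 (Section 10).
- Stated floor: 10 (Section 10).
- Assay limit L: 1 copy/mL (Sections 1 and 3.1) or 0.1 copies/mL (Section 13; same figure in Section 11). The comparison in Section 1 implies 4/30 = 0.13 to 5/30 = 0.17.
- Value given to results below L: not stated. Scoring at L is assumed, with L/√2 and L/2 as alternatives.

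**Step 1: the floor.** Lowest baseline that can show a 1-log fall = 10 x the value given to results below the limit.

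| Assay limit (copies/mL) | Scored at L | Scored at L/√2 | Scored at L/2 |
|---|---|---|---|
| 1 | 10 | 7.1 | 5 |
| 0.13 to 0.17 | 1.3 to 1.7 | 0.94 to 1.2 | 0.67 to 0.83 |
| 0.1 | 1 | 0.71 | 0.5 |

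The plan's 10 is reproduced with L = 1 and scoring at the limit. With L = 0.1 it becomes 1, a factor of ten lower. For example, a fall from 5 to 0.4 copies/mL is log10(5/0.4) = 1.10, which a 0.1 copies/mL assay can measure.

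**Step 2: largest recordable fall at L = 0.1, scored at L.** This is log10(baseline/0.1).

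| Recorded baseline (copies/mL) | 0.1 | 0.2 | 0.5 | 0.9 | 1 | 5 | 10 |
|---|---|---|---|---|---|---|---|
| Largest fall (log10) | 0.00 | 0.30 | 0.70 | 0.95 | 1.00 | 1.70 | 2.00 |

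**Step 3: are patients below the floor expected?** Yes.

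- Section 4.1 selects on cell-associated RNA and sets no lower bound on plasma RNA.
- The Précis and Section 1 anticipate patients whose plasma RNA is below detection.
- Section 13 lowers the cutoff from the 0.38 copies/mL of the earlier raltegravir study to 0.1. A patient gained between those values can show at most log10(0.38/0.1) = 0.58 log10.

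The documents give no baseline distribution, so the number below the floor is unknown. If 2, 5 or 8 of the 10 were below it, then 20%, 50% or 80% would be fixed as non-responders under the 1-log definition.

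**Step 4: effect on the baseline question (illustrative simulation).** All settings are assumptions: log10 baseline uniform between 0.1 and 50 copies/mL; half of patients with a true 1.3 log10 fall unrelated to baseline; five weekly values on the log scale; within-patient SD 0.1 to 0.3 log10; a separate baseline value as predictor, as Section 10 plans. An AUC of 0.50 means that baseline does not predict response.

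| Setting | AUC, 1-log | AUC, slope |
|---|---|---|
| No floor (SD 0.2) | 0.50 | 0.50 |
| L = 0.1, scored at L | 0.70 to 0.77 | 0.63 to 0.67 |
| L = 0.1, scored at L/2 | 0.64 to 0.70 | 0.60 to 0.62 |
| L = 1, scored at L | 0.86 to 0.92 | 0.80 to 0.86 |

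With L = 0.1 scored at L, the 1-log rule found 4 to 12% of true responders whose true baseline was below 1 copy/mL, against 71 to 94% at 1 to 10 copies/mL. The few found below 1 had a recorded baseline above 1 through assay noise. The slope rule found 25 to 43% of true responders below 1 copy/mL and 63 to 100% above.

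**The case against.** The plan sees the floor and answers it with the slope definition, and the baseline question is asked under both. That is fair, and non-response by construction applies strictly to the 1-log definition. It is only a partial answer: the 1-log definition stays in the comparison, and runs of values at the limit flatten slopes as well. The separate baseline value guards against regression to the mean and does nothing about the floor.

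The figure of 10 is not an arithmetic slip. It agrees with Sections 1 and 3.1. Section 13 describes a later gain in sensitivity, so 0.1 is better supported, but this is a conflict between sections. If 1 copy/mL does apply, the bias is larger.

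The analysis is secondary, in 10 patients, and Section 10 admits very low power. It also needs some 1-log responders before any association can appear, and Section 11 contemplates none. All of this stands and limits the importance of the point. With so few patients, however, the pattern will be read descriptively, and low power does not remove a bias.

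A reader might infer two stronger claims that the documents do not support:

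- **That patients at 1 to 10 copies/mL are treated as unable to respond.** The figure of 10 is only the reason given for a second method. A fall from 5 to 0.4 copies/mL would count as a response under Section 10 as written.
- **That the 1-log threshold is too strict and should be lowered.** Section 1 does report that "effects of interferon were modest (2-8 fold reductions in viral RNA" (0.30 to 0.90 log10) and that "HIV-1 viremia declined by a mean 0.77" log10 over 12 weeks. The first is in vitro and the second is a mean in people not on antiretroviral therapy. A mean of 0.77 does not stop individuals exceeding 1 log, and the documents give no assay variability from which to justify a smaller threshold.

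**Conclusion.** The point holds for the 1-log responder comparison. Patients whose recorded baseline is below ten times the assay limit cannot be responders under that definition. Keeping them in as non-responders produces a positive association between baseline and response from the assay limit alone. The floor is 1 copy/mL with the Section 13 limit and scoring at that limit, 0.5 with scoring at half the limit, and 10 with a 1 copy/mL limit. The direction of the bias does not depend on which of these applies. The simulated sizes rest on assumed distributions and are illustrative. The primary paired t-test is not touched by this rule.

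**What to change.** 1. Reconcile Sections 1, 3.1, 10 and 13 to one assay limit for this trial.
2. State how results below that limit are scored.
3. In Section 10, replace the floor of 10 with ten times the limit (1 copy/mL for a limit of 0.1 with scoring at the limit).
4. Report patients below that floor as not evaluable for the 1-log definition, judged on the baseline value from which the change is computed. Leave them out of the 1-log responder comparison, including the question about baseline viral load, and give their number.
5. When fitting individual slopes, treat results below the limit as left-censored.

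The cost is a few sentences in Section 10, with no new samples or patients. Fewer of the 10 participants will be evaluable for the 1-log definition, in an analysis that already has very low power. A censored slope from a handful of values will be imprecise, and it may not be estimable where most values are below the limit.
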